5.2.1 Inclusion Criteria

- Male or female, aged 21-60 years.
- A BMI categorized as overweight (≥ 25) but not stage II obesity (≤ 35)
- Daily steps < 5,000.

- Ownership of a smartphone device with either the Apple Health or Google Fit application.
- Willingness to carry their phone in their pocket or on their person at all times to track steps during study.
- Willing to download the Pro2col application and connect it with either the Apple Health or Google Fit application.
- Willingness to complete physical tasks including a timed one-mile walk/run, regular or modified push-ups to exhaustion, and chair get-ups to exhaustion.
- For the experimental group, subjects must be willing to follow the application protocol which is laid out later in this document.
- Able to read, understand, sign and date the informed consent document (English only)
- Able and willing to comply with the scheduled visit(s) and study requirements.

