10. STATISTICAL METHODS

10.1. Sample Size Determination

The targeted sample size of 50 participants was determined by the Sponsor based on a meta-analysis involving 206,873 participants (Staiano et al., 2024). This analysis demonstrated that digital health interventions led to improvements in physical activity (+1,329 steps/day), reduced sedentary behavior (-7 hours/week), and increased vigorous exercise (+1 hour/week). Using these values, we conducted a power analysis, which identified an effect size difference of 0.8 between the control and experimental groups for average changes in habits like daily steps. This analysis confirmed that a sample size of 50 subjects would be sufficient.

https://trialsjournal.biomedcentral.com/articles/10.1186/s13063-015-0950-4

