10.2. Demographics and Baseline Characteristics

Demographic information will include age, gender, height, weight, BMI, race, and ethnicity. Baseline characteristics, including health data, subjective questionnaires, and anthropometrics will be summarized by treatment.

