10.3. Analyses

10.3.1 Primary Analysis

Descriptive statistics will be reported including mean, median, minimum and maximum values, standard deviation, and 95% confidence intervals of the mean. All outcome measure data will be reported as mean \pm standard deviation (SD). Relative and absolute changes between groups for all outcomes will be reported and analyzed for statistical significance using paired *t* tests. Additionally, effect sizes will be calculated as Cohen's d_g

for between-subjects analyses as the difference between group means divided by the pooled standard deviation times a correction factor [1]. Statistical significance will be set at p < 0.05 and all analyses will be performed using SPSS Version 28.0.

Cohen's
$$d_g = \frac{\left(X_{Group A} - X_{Group B}\right)}{SD_{pooled}} \times \left(1 - \frac{3}{4 \times (N1 + N2) - 9}\right)$$

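### Section 10.3.1 tests changes without using each outcome's baseline value as a covariate and plans no confidence interval for the difference between arms: an avoidable efficiency loss of unknown size, plus a reporting gap

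*Combined protocol and SAP*

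**What the plan says.** Section 10.3.1 is the whole efficacy plan. Its testing sentence reads "Relative and absolute changes between groups for all outcomes will be reported and analyzed for statistical significance", and the test it names is the paired t test. The threshold follows: "Statistical significance will be set at p < 0.05". No regression, ANCOVA, mixed model or covariate appears.

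The only interval is in the list of descriptive statistics: "standard deviation, and 95% confidence intervals of the mean". The comparison between arms gets a p-value and a bias-corrected Cohen's d as a point estimate. Neither d nor the arm difference is given an interval.

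The baseline values exist. Sections 4.1 and 4.2 schedule the primary and secondary outcomes before and after the intervention. Section 10.2 uses baseline data only descriptively: "Baseline characteristics, including health data, subjective questionnaires, and anthropometrics will be summarized by treatment".

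**The concern.** A paired t test contrasts pre with post in the same people, so it does not compare PRO with CON. The obvious repair is a two-sample t test on the changes, but that would leave both omissions in place. Subtracting the baseline fixes its coefficient at 1, whereas a model with baseline as covariate estimates the coefficient from the data. When the true slope is not 1, fixing it adds variance to the arm difference.

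Two things are at stake in a pilot with a floor of 50 participants and a target of at least 20 completers per arm (Section 5.1). One is power that could be had without further subjects or data. The other is the result a pilot is best placed to deliver: the estimated arm difference with its uncertainty.

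**Working it through.** **Inputs.** From the documents:
- Section 10.1: an "effect size difference of 0.8 between the control and experimental groups for average changes in habits like daily steps", and "This analysis confirmed that a sample size of 50 subjects would be sufficient". It also cites "improvements in physical activity (+1,329 steps/day" but gives no SD.
- Section 10.3.1: the 0.05 level.
- Section 5.1: at least 20 completers per arm.

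Assumed, because the documents do not state them: a two-sided test, 80% power, 1:1 allocation, the pre-post correlation r, and the ratio of post SD to baseline SD.

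**Step 1: the plan's own figure.** For an unadjusted two-sample comparison, n per arm = 2(1.960 + 0.842)² / 0.8² = 24.5, rounded up to 25, so 50 in total. This matches. By noncentral t, power at d = 0.8 is 79% with 25 per arm and 69% with 20 per arm. This two-sample test on change is the comparator below. The plan does not name it, but its sample size fits it.

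**Step 2: variance saved by adjustment.** Let b be the slope of post on baseline.
- Variance of change = residual variance + (1 − b)² × baseline variance.
- Variance after adjustment = residual variance.
- Variance saved = (1 − b)² × baseline variance, which is never negative and is zero at b = 1.

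With baseline SD 1 and post SD k, b = rk, the change variance is 1 + k² − 2rk, and the adjusted variance is k²(1 − r²). At k = 1 the ratio reduces to (1 + r)/2.

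**Step 3: power.** The effect becomes 0.8/√ratio, with 2n − 3 degrees of freedom.

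| r | k | Variance ratio | Power, 25 per arm (change: 79%) | Power, 20 per arm (change: 69%) |
|---|---|---|---|---|
| 0.3 | 1 | 0.65 | 93.0% | 86.3% |
| 0.5 | 1 | 0.75 | 89.2% | 81.2% |
| 0.7 | 1 | 0.85 | 85.2% | 76.2% |
| 0.9 | 1 | 0.95 | 81.1% | 71.5% |
| 0.3 | 2 | 3.64/3.80 = 0.96 | 81% | – |
| 0.5 | 2 | 3.00/3.00 = 1.00 | 79% | – |
| 0.7 | 2 | 2.04/2.20 = 0.93 | 82% | – |

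A simulation of 20,000 trials per setting with equal variances gave adjusted power of 85%, 80%, 75% and 70% at 20 per arm for r = 0.3, 0.5, 0.7 and 0.9. Type I error was near 5% for both methods.

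**Step 4: the interval the plan does not ask for.** For changes, the 95% half-width is t × √(2/n) in SD of change: 2.011 × √(2/25) = 0.57 at 25 per arm, and 2.024 × √(2/20) = 0.64 at 20. If 1,329 steps/day is taken as the 0.8 SD effect (an assumption), the SD of change is 1,329/0.8 = 1,661. The half-widths are then about 945 and 1,063 steps/day.

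**The case against.** The strongest reply is that nothing here is invalid. A between-arm comparison of changes is unbiased under randomisation, and its standard error already reflects chance baseline imbalance. Any shift from such imbalance is therefore not a second harm on top of the variance ratio. The size of the gain also rests on quantities absent from the documents: it is about 2 power points at r = 0.9 with equal variances, and nil at r = 0.5 with k = 2. The primary outcomes will not share one r. Enrolment may reach 200, and at 100 per arm an effect of 0.8 already has over 99.9% power. All of this stands, and it limits the size of the point but not its direction.

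Three stronger readings are tempting, and the documents support none of them.

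- **Daily steps as the worst case.** The entry criterion "Daily steps < 5,000" narrows the baseline range and lowers r, so a reader might infer that steps lose most. Under a linear model, however, selecting on baseline leaves b and the residual variance alone and shrinks the baseline variance, so the loss falls. With assumed b = 0.7 and equal variances, the ratio is 0.51/(0.51 + 0.09) = 0.85. With a quarter of that baseline variance, r drops to 0.44 but the ratio rises to 0.51/(0.51 + 0.0225) = 0.96.
- **Change over-corrects whenever r is below 1.** The condition is b = r × (post SD / baseline SD) below 1. At k = 2 and r = 0.5, b is exactly 1. Section 6.2 moves PRO subjects towards 10,000 steps, so a post SD above the baseline SD is plausible.
- **The missing interval discards precision.** It does not. It leaves imprecision unreported, and a reader could derive an interval if means, SDs and arm sizes are given for the changes.

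It is also fair to say that the paired-test wording is the graver fault in the sentence, and that Section 10.3.1 tests relative as well as absolute changes. The algebra above covers absolute changes only.

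**Conclusion.** The point holds as an efficiency loss and a reporting gap, and should be corrected. It is not a bias. Section 10.3.1 leaves the collected baseline values out of the comparison and requires no interval for the arm difference. Under equal variances, adjustment is worth about 2 to 14 power points at 25 per arm for r from 0.9 down to 0.3. With the post SD twice the baseline SD, it is worth 0 to 3 points for r from 0.3 to 0.7. These figures assume a two-sided 5% level, 1:1 allocation, an effect of 0.8 SD of change, and a two-sample test on change in place of the paired test that is written. The direction needs no assumed r or variance ratio; the size cannot be fixed without them.

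**What to change.** In Section 10.3.1, replace the paired t tests for the between-arm comparison of each continuous outcome with a linear model of the post value on arm and that outcome's baseline value. Report the adjusted PRO minus CON difference with its 95% confidence interval. Keep absolute and relative changes as descriptive summaries by arm.

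The cost is one paragraph of wording and one degree of freedom per model. The model is standard in the software already named, and no new data or subjects are needed. The same edit removes the paired-test wording from the comparison between arms.

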4. OUTCOMES MEASURE

- 4.1. Primary Outcomes these measures will be taken at week 0 (pre) and week 7 (post)
 - Healthspan, as assessed via a digital score within the application software.
 - **Biological Age**, as assessed via an algorithm sourced within the application.
 - Lifestyle Risk Factors, as assessed via questionnaires within the application.
 - Energy and Vitality, as assessed via questionnaires within the application.
 - Strength and Endurance, as assessed by performance measures including a timed mile walk/run, push-ups to exhaustion, and chair get-ups to exhaustion.
 - Body Composition, as assessed via a previously validated digital scale.
 - Blood Pressure, as assessed via an electronic blood pressure cuff.
 - Lifestyle Habits, as assessed by specific interfaces within the application and guided by an AI "coach."
 - **Daily Steps**, as collected via the Apple Health or Google Fit application on the subject's pre-existing personal device.

4.2. Secondary Outcomes – these measures will be taken at week 0 (pre) and week 7 (post)

- **Depression**, as assessed by the previously validated PHQ-9 subjective questionnaire.
- Quality of Life, as assessed by the previously validated SF-36 subjective questionnaire.

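### Nine unranked primary outcomes are each tested at p < 0.05 with no hierarchy or adjustment; one should be named before data are seen

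*Combined protocol and SAP*

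**What the plan says.** Section 4.1 opens with "Primary Outcomes these measures will be taken at week 0 (pre) and week 7 (post") and then gives nine bullets: Healthspan, Biological Age, Lifestyle Risk Factors, Energy and Vitality, Strength and Endurance, Body Composition, Blood Pressure, Lifestyle Habits and Daily Steps. None is marked as leading. Section 4.2 adds two secondary outcomes.

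Section 10.3.1 covers them all together: "Relative and absolute changes between groups for all outcomes will be reported and analyzed for statistical significance using paired" t tests. It adds a between-group effect size and one threshold: "Statistical significance will be set at p < 0.05 and all analyses will be performed using SPSS Version 28.0". It mentions no ordering, adjustment or designated lead.

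On sample size, section 10.1 states: "The targeted sample size of 50 participants was determined by the Sponsor". Its power analysis "identified an effect size difference of 0.8 between the control and experimental groups for average changes in habits like daily steps", and it concludes: "This analysis confirmed that a sample size of 50 subjects would be sufficient". It gives no power, no sidedness, and no statement of whether the 50 are enrolled or analysed. Section 5.1 allows up to 200 enrolled, sets 50 meeting the inclusion criteria as a minimum, and accepts 20 completers per group.

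**The concern.** When nine outcomes all count as primary and each has its own 5% test, any one of them crossing the threshold can be presented as a positive primary result. If the app changes none of them, the chance of at least one such result is well above 5%. Nothing in the plan fixes in advance which result leads the report. The trial is also unblinded (section 6.4), and several primaries are app-generated scores or self-reports, so a clear lead outcome matters more. Enrolling toward 200 does not help, because the false-positive rate of a valid test does not fall with sample size.

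The sample-size statement is a lesser matter. A reader of section 10.1 cannot tell what power the sponsor regards as sufficient, or what power remains at the completer minimum that section 5.1 accepts.

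**Working it through.** **Inputs**
- Primary outcomes: 9 (section 4.1).
- Threshold: 0.05 per test (section 10.3.1).
- Effect size 0.8 and target of 50 (section 10.1).
- Minimum of 20 completers per group and maximum of 200 enrolled (section 5.1).
- Assumed, because the documents do not say: one valid two-sided between-group test per outcome, 1:1 allocation, and a common correlation between outcomes. Section 10.3.1 names paired t tests for a between-group comparison; that is a separate problem and is set aside here.

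**1. The plan's figure of 50**

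Normal approximation, two-sided 0.05, assumed 80% power: n per arm = 2(1.960 + 0.842)² / 0.8² = 24.5, so 25 per arm and 50 in total. The t-test version gives 25.5, so 26 per arm and 52 in total. The figure therefore reproduces as 50 analysed.

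Two other routes also lead to 50, read as enrolled with 20% loss (40/0.8 = 50):
- one-sided, 80% power: 2(1.645 + 0.842)² / 0.64 = 19.3, so 20 per arm;
- two-sided, 70% power: 2(1.960 + 0.524)² / 0.64 = 19.3, so 20 per arm.

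The text does not say which was meant.

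**2. Chance of at least one false-positive primary**

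Independent tests: 1 − 0.95⁹ = 0.370. Correlated tests: write each statistic as √ρ·U + √(1−ρ)·E, with U shared by all outcomes. The rate is 1 minus the average over U of P(|Z| < 1.96 given U) raised to the number of tests.

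| Common correlation | Nine tests | Eight tests |
|---|---|---|
| 0 | 37% | 34% |
| 0.3 | 33% | 30% |
| 0.5 | 27% | 25% |
| 0.7 | 20% | 19% |
| 0.9 | 12% | 12% |

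The eight-test column drops one outcome: "Lifestyle Habits, as assessed by specific interfaces within the application and guided by an AI" coach, which the control group is not described as receiving.

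The count can also go up. Strength and Endurance has three tests and blood pressure has two values, so counting each separately gives 9 + 2 + 1 = 12, and 1 − 0.95¹² = 0.460 if independent. Analysing both relative and absolute change would add more.

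Counting only results that favour the app, nine tests give 1 − 0.975⁹ = 20% if independent and 6% at correlation 0.9, against 2.5% for one primary.

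Simulated two-group t tests on nine outcomes agree, and show no dependence on sample size: 37.1% (20 per arm) and 36.9% (100 per arm) if independent; 12.6% and 12.4% at correlation 0.9.

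**3. Power at effect size 0.8, independent-groups t test, 0.05**

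| Analysed per arm | Two-sided | One-sided |
|---|---|---|
| 20 | 69% | 80% |
| 25 | 79% | 87% |
| 100 | above 99% | above 99% |

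The normal approximation gives 72% and 81% two-sided at 20 and 25 per arm.

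**The case against.** The strongest defence is that this is a pilot whose stated aim is to explore effects (sections 3.1 and 5.1), and that section 10.3.1 commits to reporting every outcome with effect sizes. Full reporting lets a reader see how many tests were done. This lowers the severity. It does not settle the matter, because all nine outcomes still carry the primary label and a significance rule, and section 10.1 claims a sufficient sample. A smaller change, calling every p-value nominal and exploratory, would remove most of the risk of false claims but would leave the trial with no lead result.

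A reader might infer more than the documents support in four places:
- *That this trial's error rate is 37%.* That figure needs nine independent tests. Healthspan and Biological Age come from one formula (Appendix 1), so some correlation is certain, its size is unknown, and the count itself is open in both directions.
- *That 50 must mean analysed, or that the trial misses its power target.* Section 10.1 states no power to miss. Section 5.1 treats 50 as a minimum meeting the inclusion criteria, and the status table in section 7.6 defines enrolled in nearly those terms. The 69% is a floor at the accepted minimum, not the expected power, and larger enrolment within the permitted 200 would remove the shortfall.
- *That control-arm steps have no route into the data.* Section 5.2.1 requires every subject to be willing to download Pro2col and connect it, although section 5.1 describes only the experimental group as enrolled in it. The route needs confirming; it is not shown to be absent.
- *That the protocol has already chosen steps.* Section 10.1 mentions steps only as an example of a habit.

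**Conclusion.** The multiplicity point holds and should be fixed. With nine unranked primaries each tested at 0.05, the chance of at least one false-positive primary is somewhere around 12% to 37% for common correlations from 0.9 down to 0, against 5% for a single primary. The range rests on one valid between-group test per outcome and an assumed common correlation. It illustrates the size of the problem and is not an estimate for this trial. Even the most favourable case shown is more than twice 5%.

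The sample-size point is only a request for clarification: section 10.1 leaves out the power, the sidedness and the meaning of 50. The documents do not support a finding that the trial is underpowered.

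**What to change.** Before data are seen, name one primary outcome in section 4.1. A reasonable candidate is the between-arm difference in change in average daily steps from baseline to post-test. Steps are device-recorded ("as collected via the Apple Health or Google Fit application on the subject's pre-existing personal device") and are the listed primary that section 10.1 gives as its example. State the averaging window, and use the same window and data source in both arms. Reconcile sections 5.1 and 5.2.1 by confirming that control-arm steps are captured the same way.

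In section 10.3.1, limit the p < 0.05 claim to that primary. Report the other eight outcomes as secondary estimates with 95% confidence intervals, and label any p-values nominal and exploratory. The two existing secondary outcomes would then carry no significance claim either.

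In section 10.1, state the power, the sidedness, and whether 50 means enrolled or analysed, and give the power at 20 completers per group.

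Cost: text changes to three sections, through an amendment approved by the IRB/IEC under section 12.1, with no new visits or measurements. Naming a primary needs no extra subjects. If the sponsor answers that 50 means analysed, enrolment would have to exceed 50 to cover losses (at 20% loss, 50/0.8 = 62.5, so 63). The downside is fewer headline primary results, and an app effect seen only on other outcomes would be reported as secondary.

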10.3.2 Interim Analysis

There will be no interim analysis.

10.3.3 Safety Analysis

All safety analyses and summaries will be based on the Safety population. The number and percentage of subjects reporting AEs during the study will be tabulated and summarized. Subjects experiencing serious adverse events, treatment-related adverse events, and discontinuation from the study due to adverse events will also be summarized. Treatment-related adverse events will include events marked as being at least possibly or probably related to the study dose. Adverse events will be presented by severity and by relation to treatment. Enrollment status with respect to number of subjects enrolled, completed, lost-to-follow and discontinuation regardless of reason will be presented. All adverse events and concomitant medications will be presented in listings.

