3.3. Exploratory Objectives

• Record any adverse event (AE) experienced by study subjects after enrollment in the digital application.

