5. INVESTIGATIONAL PLAN

5.1. Overall Study Design and Plan

This is a non-blinded randomized controlled pilot trial conducted over up to 8 weeks. Week 0 will involve baseline measurements and enrollment, Weeks 1-6 constitute the intervention, and Week 7 to 8 is reserved for post-testing. The study will enroll up to 200 participants, with a minimum of 50 participants who meet the inclusion criteria, and a minimum target of 20 participants completing the study in each group (experimental and control).

Participants will be recruited from across the United States using a decentralized electronic database. The study will include individuals aged 21-60 with a BMI \geq 25 (overweight) and \leq 35. Additionally, qualified subjects must have current daily activity records that show an average daily step count under 5,000. Participants must also be free of disease and must own either a personal smartphone device with the Apple Health or Google Fit application. Finally, participants must be willing to keep their device with them at all times to ensure accurate activity tracking.

Following baseline testing and enrollment in the study, participants will be randomly assigned to either the control (CON) or experimental (PRO) group. The control group will receive subject-facing materials depicting current general activity recommendations as published by the American Heart Association (AHA) and current dietary guidelines provided by the United States Department of Agriculture (USDA). The experimental group will be enrolled in the Prime Health Technologies software (Pro2col), which provides a digital diagnostic score to calculate healthspan and biological age, along with AI and group community-based coaching dynamics. Subjects will be assigned a 6 week progressive protocol targeting improvements in daily activity levels, nutritional awareness, and overall lifestyle risk factors. Both groups will then be monitored by study staff throughout the duration of the intervention period with post-testing taking place following the last week of the experiment.

Due to the remote nature of subject recruitment, no in-person facility visits are required for participants.

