7.2. BASELINE TESTING

Subjects who continue to be eligible for this study will then complete baseline testing. Subjective questionnaires will be provided to assess items such as current activity levels, nutrition habits, and lifestyle factors related to health and wellness. Enrolled and randomized subjects will also receive a blood pressure cuff and digital scale to record blood pressure and bodyweight/body composition, respectively. Moreover, subjects will complete electronic calculations to estimate their healthspan and biological age. Finally, subjects will perform three physical fitness tests, including:

- Timed one mile walk/run
- Push-ups (or modified push-ups for women) to exhaustion
- Chair get-ups to exhaustion

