7.3. INTERVENTION

Subjects will follow their assigned condition for 6 weeks. Subjects in the control group will be monitored by study staff but otherwise uninstructed in regard to activity and nutrition. Their adherence to the provided educational materials is entirely up to them. The experimental group will be initiated into a 4-6-week (28-42 days depending on subject availability for the last testing day) progressive protocol on the Pro2col app. They will receive daily updates, notification, and education regarding healthy habits such as exercise, hydration, and improved nutrition practices. An AI coach will be responsible for providing instructions and feedback to all application users.

7.4. **POST-TESTING**

Subjects who complete the 4-6-week (28-42 days depending on subject availability for last testing day) intervention and continue to be eligible for this study will then complete post testing. Subjective questionnaires will be provided to assess items such as current activity levels, nutrition habits, and lifestyle factors related to health and wellness. Enrolled and randomized subjects will also receive a blood pressure cuff and digital scale to record blood pressure and bodyweight/body composition, respectively. Moreover, subjects will complete electronic calculations to estimate their healthspan and biological age. Finally, subjects will perform three physical fitness tests, including:

- Timed one mile walk/run
- Push-ups (or modified push-ups for women) to exhaustion
- Chair get-ups to exhaustion

Finally, upon completion of the study (or early withdrawal), subjects will be directed to delete the investigational application from their smart device, and no further data will be collected.

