9.2. Reporting Period

Serious adverse events require immediate notification within **24 hours** to the IRB and its designated project manager. When reporting a serious adverse event, the investigator or designee completes the SAE form with as much information as possible however, at a minimum the Subject ID, Name of INP, SAE, and Name of person reporting the event.

All adverse events (serious and non-serious) must be collected on the subject's case report form (CRF) from the time the subject signed informed consent through the last subject visit.

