9.3. Definition of an Adverse Event

An adverse event is any untoward medical occurrence in a clinical investigation associated with the use of an investigational product in human subjects. The event need not necessarily have a suspected causal relationship with the treatment or usage.

Examples of adverse events include but are not limited to:

- Clinically significant symptoms and signs
- Changes in physical examination findings

• Hypersensitivity

Additionally, they may include the signs or symptoms resulting from:

- Product misuse
- Product dependency
- Extravasation
- Study related procedure (e.g., resistance training protocol)

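### The any-AE percentage in section 10.3.3 has no onset cut-off, so events from the baseline exhaustion tests count the same as intervention-period events and would pull an arm comparison together

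*Combined protocol and SAP*

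**What the plan says.** - **Measure.** Section 10.3.3: "The number and percentage of subjects reporting AEs during the study will be tabulated and summarized". It sets no onset window and gives no exposure measure. It rests on a population that is named but not defined: "All safety analyses and summaries will be based on the Safety population".
- **Collection window.** Section 9.2 requires all adverse events (AEs) to be recorded "from the time the subject signed informed consent through the last subject visit". Section 9.3 includes signs and symptoms arising from study procedures.
- **A second window.** The exploratory objective in section 3.3 reads: "Record any adverse event (AE) experienced by study subjects after enrollment in the digital application".
- **Tests before the intervention.** Section 7.2: "Finally, subjects will perform three physical fitness tests, including" a one-mile walk/run, push-ups and chair get-ups. Appendix 1 takes the last two to muscle failure. Section 7.4 repeats all three at post-testing.
- **Order of events.** Section 5.1: "Following baseline testing and enrollment in the study, participants will be randomly assigned to either the control (CON) or experimental (PRO) group". Sections 7.1 and 7.2 read as if assignment is already known by then. Section 5.1 puts baseline in Week 0 and the intervention in Weeks 1-6.
- **Length of follow-up.** Section 7.3 opens: "Subjects will follow their assigned condition for 6 weeks". It then gives the experimental group 28-42 days. Section 7.4 gives 28-42 days without naming an arm.
- **Other safety output.** Section 10.3.3 also plans summaries of serious AEs, treatment-related AEs and AE discontinuations, a presentation by severity and by relation, disposition counts, and full listings.

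**The concern.** Collecting AEs from consent is right. The difficulty is in analysing them as one pool. The trial selects people walking under 5,000 steps a day and asks them for maximal efforts in Week 0. Section 6.5 names musculoskeletal injury, fatigue and dizziness as risks of physical fitness programs. Neither condition can cause an event that precedes it, yet such an event makes the subject a case in the any-AE percentage. That subject cannot be counted again for a later event, so baseline-test events add the same background to both arms and hide part of any excess under the app programme. What is at stake is how far the overall AE percentage can be read as a comparison of the two conditions.

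**Working it through.** **The plan's own figure.** No AE rate or safety power is stated, so there is none to reproduce. The only design figure is the total of 50 in section 10.1, for an effect size of 0.8. Assuming a two-sided 5% test, 80% power and 1:1 allocation (power, sidedness and ratio are not stated):

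n per arm = 2 × (1.960 + 0.842)² / 0.8² = 24.5, rounded up to 25, or 50 in total.

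The noncentral t version gives 26 per arm, 52 in total. This serves below only to give the scale of an arm of 25.

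**Does a baseline-test event enter the percentage?**
1. The tests come after consent, so their events fall inside the section 9.2 window.
2. Procedure-related events are AEs under section 9.3.
3. The tests are in Week 0, before the assigned condition starts, whether randomisation precedes or follows them.
4. Section 10.3.3 has no onset cut-off, so a subject who has such an event and continues is counted.

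**Size of the dilution.** Let b be the share with a baseline-test event, equal in both arms, and let c and p be the intervention-period risks in control and experimental subjects without one. (Under independence these are simply the risks in each arm.)

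- Any-AE share: control 1 − (1 − b)(1 − c); experimental 1 − (1 − b)(1 − p).
- Risk difference: (1 − b)(p − c).

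Assumed c = 10% and p = 20%:

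| b | Control | Experimental | Difference (points) | Risk ratio |
|---|---|---|---|---|
| 0% | 10.0% | 20.0% | 10.0 | 2.00 |
| 2% | 11.8% | 21.6% | 9.8 | 1.83 |
| 5% | 14.5% | 24.0% | 9.5 | 1.66 |
| 10% | 19.0% | 28.0% | 9.0 | 1.47 |
| 20% | 28.0% | 36.0% | 8.0 | 1.29 |

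For example, at b = 20%: control 1 − 0.8 × 0.9 = 28%; experimental 1 − 0.8 × 0.8 = 36%; 36 − 28 = 8 points; 36/28 = 1.29. In an arm of 25, the excess falls from 2.5 subjects to 2.0. At b = 2% it falls to 2.45.

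Counting only onset from the start of the assigned condition returns the first row.

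**Follow-up, as a bound only.** If every experimental subject were observed for 28 days and every control subject for 42, a constant hazard giving 20% in control would give 1 − 0.8^(28/42) = 13.8% in the experimental arm with no difference in risk. The largest distortion of the hazard is 42/28 = 1.5-fold. If both arms vary alike over 28-42 days, the expected bias from planned duration is nil.

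**The case against.** The best defence is that the overall percentage does not stand alone. Section 9.6 requires a causality assessment for every AE, and an investigator would normally mark a baseline-test injury as unrelated, so it would leave the treatment-related summary. The listings show the rest. This stands in part. However, the trial is unblinded (section 6.4), so causality is judged with the arm known once assignment is made. Section 9.6 also handles events of unknown cause as related, and section 10.3.3 defines relatedness by reference to a study dose that an app trial does not have. Onset date does not depend on such a judgement.

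It is also fair that section 10.3.3 does not state a split by arm and plans no test or risk ratio for AEs. The Safety population is undefined, and a subject injured before randomisation who then withdraws may belong to no arm. The dilution therefore applies if the table is read by arm, and to subjects who continue.

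Three stronger readings are tempting, and the documents do not support them:
- A reader might infer that this is the trial's only safety analysis. It is not, given the other summaries and listings in section 10.3.3.
- A reader might infer that every event is counted. The measure counts subjects, and the dilution depends on that.
- A reader might infer from section 7.3 that the experimental arm is observed for less time and so looks safer. Section 7.4 applies 28-42 days without naming an arm and ties the variation to availability for the last testing day.

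Crude percentages are defensible in a small pilot, so person-time is supportive here and not a replacement.

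**Conclusion.** The point holds. As written, the any-AE percentage mixes events that precede the assigned condition with those that follow its start, and a by-arm comparison of it would understate any excess. The loss on the risk difference is the share b itself: 2% of the excess at b = 2%, 20% at b = 20%. The risk ratio moves more, from 2.0 to between 1.83 and 1.29 over the same range. These figures rest on assumed risks of 20% v 10%, an assumed range for b, and equal b in both arms. If baseline-test events are rare, the practical effect is small.

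A between-arm bias from unequal follow-up or differential withdrawal is possible but not established. The two AE windows and the follow-up lengths are inconsistent in the text and need to be reconciled. The section 3.3 window is also hard to apply to controls: section 5.1 enrols only the experimental group in the software, while section 5.2.1 asks all subjects to be willing to download it.

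**What to change.** In section 10.3.3:

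1. Define the Safety population, and state that the AE tables are presented by arm.
2. Tabulate by arm the number and percentage of subjects with an AE whose onset is on or after the first day of the assigned condition.
3. Show AEs from consent to that day in a separate table.
4. Flag events on or just after the post-test day, because the same tests are repeated then.
5. Give person-weeks of observation by arm beside the percentages, as a supportive figure, since observation may run from 28 to 42 days and withdrawals are observed for less.

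Elsewhere, reconcile the AE window in section 3.3 with section 9.2, and the follow-up lengths in sections 7.3 and 7.4. Collection from consent stays as it is.

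Cost: amended wording and one extra table, using AE onset dates and the start and end dates of each subject's intervention and observation. No new subjects or procedures are needed.
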